2.1. Aims

2.1.1 Primary

- Characterise the pharmacokinetics of oral intermediate dose micronised progesterone in comparison to that achieved by iv dosing in the literature (Stage 1) after a single dose of 200mg and 600mg of micronised progesterone and Stage 2 after repeated (TDS) administration at a dose to be determined. Establish the acceptability, tolerability and safety of a dose of micronised progesterone that achieves the target drug exposure (Stage 2)

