2.2. Endpoints

2.2.1 Stage 1

2.2.1.1 Primary:

Pharmacokinetic profile (including C_{max}, Cl and AUC) of micronised progesterone after single doses of 200mg and 600mg in >4 of 6 patients that allow estimation of serum progesterone exposure (AUC) that is 50 – 150% of that targeted in order to determine the dose in Stage 2..

2.2.2 Stage 2

2.2.2.1 Primary:

- ≥ 13 of 18 patients able to tolerate micronised progesterone until the end of the 14-day treatment period at a dose predicted to achieve the target progesterone exposure.
- Trough progesterone concentrations within 50 – 150% of target

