9. SUCCESS CRITERIA AND BARRIERS TO PROPOSED WORK

9.1 Success criteria

The PROSSPER trial will have been successful if it generates results that underpin a subsequent definitive Phase 3 efficacy trial by

- Defining the oral dose of micronised progesterone required to reach target serum levels
- Confirming the acceptability, tolerability and safety of micronised progesterone, at the selected dose, in this patient population
- Verifying the acceptability and utility of the dexamethasone dose reduction protocol
- Collecting QoL data and PROMs relevant to the symptoms of raised intracranial pressure and dexamethasone side effects
- Demonstrating possible efficacy of micronised progesterone in reducing the dose of dexamethasone needed to control symptoms of cerebral oedema
- Establishing that a Phase 3 trial would be feasible and acceptable to patients.

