11.3 Micronised progesterone/placebo (IMP)

Micronised progesterone/placebo is the trial IMP and will be provided by the manufacturer as 200mg capsules. Progesterone/placebo should be taken orally within 30 minutes of finishing a meal.

Stage 1: Day 1-10 (Please refer to Appendix No.6 - Doses Stage 1)

On Day 1, patients will take 200mg micronized progesterone in the morning after breakfast (08.00 - 10.00).

A further dose of 600mg of micronized progesterone will be taken on another day between Days 5-10. This day will be decided by the clinical team and patient.

Stage 2: Day 1-22 (Please refer to Appendix No.7 - Doses Stage 2)

The Stage 2, Day 1 starting dose of micronized progesterone/placebo will be determined by the pharmacokinetic results of Stage 1.

In Stage 2, patients will also take progesterone/placebo at 08.00 - 10.00 (breakfast), 12.00 – 14.00 (lunch) and 17.00 – 19.00 (dinner). Patients will record the time each meal is completed and micronised progesterone (or placebo in Stage 2) taken.

Patients will continue on this dose to Day 14 unless they do not tolerate this initial micronised progesterone/placebo dose due to side-effects. In that case, the dose of micronized progesterone/placebo will be reduced by 200mg; if that reduced dose is not tolerated, it will be reduced by a further 200mg. If the second reduced dose is not tolerable, the patient will be withdrawn from the study. For example, if the initial dose of micronized progesterone/placebo was 600mg t.d.s (three times a day) i.e. 1800 mg/day, the first dose reduction would be 400mg t.d.s, i.e. 1200mg/day in total and further dose reduction would be 200mg t.d.s. i.e. 600mg/day in total.

See Appendix 6 [Drug Table Stage 1] and Appendix 7 [Drug Table Stage 2]) for Drug tables.

Day 15-22 involves trials procedures but not micronized progesterone/placebo.

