15.5 Analysis Plan

The final analysis will be performed on the evaluable population (that is, patients who successfully completed the 14-day treatment period and were not subsequently found to be ineligible); no interim analysis is planned. Unless otherwise stated, 80% confidence intervals will be used; 1-sided p-values calculated and $\alpha=0.05$ as a threshold for significance. Substantial missing data (i.e., missing in >10% patients) will be highlighted in statistical study reports but not imputed. A full statistical analysis plan will be developed prior to any analyses being performed.

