14.4 Final analysis

The final analyses will be performed once the end of study has been declared. They will address each endpoint explicitly with evidence, including:

- Stage 1, primary endpoint (Section 2.2.1.1 Primary:) – to be assessed at end of Stage 1
 - Percentage of target exposure for each patient will be calculated and presented. Subsequent counts of number of patients to achieve 50-150% of target exposure will be presented.
- Stage 2, primary endpoint (Section 2.2.2.1 Primary:) – to be assessed at end of Stage 2
 - Number of patients tolerating progesterone until the end of the 14-day treatment period will be calculated and presented. Note that at least 13/18 patients should

be identified as tolerating progesterone (i.e., ensuring that >50% patients, using 80% CI, tolerate the treatment).

- Stage 2, secondary endpoint (Section 2.2.2.2 Secondary) – to be assessed at end of Stage 2
 - Compliance data will be presented and the number of patients complying with protocol guidelines on dose reduction will be calculated and presented. Note that at least 13/18 patients should be identified as complying with the dose reduction guidelines, to demonstrate compliance (i.e., ensuring that >50% patients, using 80% CI, comply).
 - Dexamethasone related side-effects will be coded according to the CTCAE toxicity criteria. These data will be presented in several ways, including worst value over the trial period for each patient and tabulation of all side-effects graded \geq grade 1 in at least 10% of patients.
 - Presentation/analysis of QoL (DSQ-C, EORTC QLQ-30 & BN20) data.
 - Calculation of percentage reduction in dexamethasone at Day 14.
 - Comparison of final dexamethasone dose in the progesterone and placebo arms (e.g., by ordered logistic regression).
 - Comparison of cumulative dexamethasone dose in the progesterone and placebo arms (e.g. by ANOVA/t-test or Mann Whitney U if normality assumptions are violated).
 - Comparison of time to reach final dose in each arm in the progesterone and placebo arms (e.g., Cox regression).
- Stage 2, tertiary endpoint (Section 2.2.2.3 Tertiary) – to be assessed at end of Stage 2
 - Presentation of relevant lab results to assess endocrine, liver function and lipid profiles in patients on progesterone.
 - Comparison (progesterone v placebo) of CT/MRI data (including tumour size, enhancement pattern etc)

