Appendix 7 – Stage 2: Drug table

Day	DEX dose ¹ (non IMP)	PROG/Placebo dose ² (IMP)	
1	8mg	Xmg	Dose of progesterone (Xmg) will be determined by the pharmacokinetic results of Stage 1
2 – 14	as clinically indicated, using Prossper DEX dosing	as defined by Stage 1. As clinically indicated, using Prossper PROG/Placebo dosing	
15	as clinically indicated, at clinicians discretion		
16	as clinically indicated, at clinicians discretion		
17	as clinically indicated, at clinicians discretion		
18	as clinically indicated, at clinicians discretion		
19	as clinically indicated, at clinicians discretion		
20	as clinically indicated, at clinicians discretion		
21	as clinically indicated, at clinicians discretion		
22	as clinically indicated, at clinicians discretion		

¹ DEX dosing - 8mg, 6mg, 4mg, 2mg, 0mg

From Day 3-14, if clinically appropriate, the dexamethasone dose can be reduced by 2mg/day on alternate days, and can be discontinued if indicated. Should symptoms of raised intracranial pressure recur, the dose of dexamethasone will be increased by 4mg (i.e. to 2mg above the dose at which the patient’s symptoms had been controlled).

² PROG dosing - 600mg t.d.s, 400mg t.d.s, 200mg t.d.s

Any patient unable to tolerate the initial Progesterone/placebo dose would have the dose reduced; if that reduced dose is not tolerated, it will be reduced further. If this second dose is not tolerable, the patient will be withdrawn from the study.

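### The Stage 2 tolerability count in Section 14.4 leaves out the dose condition of primary endpoint 2.2.2.1, so a patient finishing on a dose too low for the exposure target could count towards 13/18

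*Protocol*

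**What the plan says.** Section 2.2.2.1 sets the first Stage 2 primary endpoint: at least 13 of 18 patients tolerate progesterone to the end of Day 14 "at a dose predicted to achieve the target progesterone exposure". The primary aim in 2.1.1 likewise concerns tolerability of a dose that reaches the exposure target, and success criterion 9.1 reads "Confirming the acceptability, tolerability and safety of micronised progesterone, at the selected dose, in this patient population".

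Section 14.4 (Final analysis), under a bullet that refers to 2.2.2.1, gives the counting rule as "Number of patients tolerating progesterone until the end of the 14-day treatment period will be calculated and presented". It repeats the 13/18 threshold and explains it as showing that more than half of patients tolerate treatment, judged by an 80% confidence interval. It names no dose.

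The population in 15.5 is "patients who successfully completed the 14-day treatment period and were not subsequently found to be ineligible", again without reference to dose.

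Section 11.3 lowers the dose by 200 mg if the starting dose is not tolerated, and "if that reduced dose is not tolerated, it will be reduced by a further 200mg". Withdrawal follows only if the second reduced dose fails. Appendix 7 lists "PROG dosing - 600mg t.d.s, 400mg t.d.s, 200mg t.d.s" and adds "If this second dose is not tolerable, the patient will be withdrawn from the study". The Stage 2 starting dose is left to the Stage 1 results.

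**The concern.** The endpoint and the rule that evaluates it are worded differently, and 11.3 makes the difference matter. A patient whose dose is cut twice for side-effects can still reach Day 14. Read literally, 14.4 counts that patient as a success, although he or she has not shown tolerance of a dose expected to reach the exposure target. The 13/18 result is meant to support the dose for a definitive trial.

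Two neighbouring provisions do not correct the count. The >20% toxicity rule in Section 10 counts withdrawals, and a dose-reduced completer does not withdraw. The trough endpoint, the second bullet of 2.2.2.1, can reveal low exposure, but it carries no patient count and does not alter the 13/18 figure.

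A smaller, conditional matter concerns the reduction rule. It is written as two 200 mg steps with no stated floor, and its worked example starts at 600 mg t.d.s. Section 1.5.3 contemplates 600–1800 mg/day in three doses, that is 200–600 mg t.d.s., so a lower start is possible.

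**Working it through.** **Inputs.** n = 18 per arm (15.4); threshold 13, reference proportion 50% and 80% interval (14.4, 15.5); reduction steps of 200 mg per dose (11.3); levels 600, 400 and 200 mg t.d.s. (Appendix 7); exposure window 50–150% of target (2.2.1.1 for AUC, 2.2.2.1 for trough).

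**1. The protocol's own threshold.** The exact (Clopper-Pearson) two-sided 80% lower limit for x/18 is the 10th percentile of a Beta(x, 18 − x + 1) distribution.

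- 12/18: Beta(12, 7) gives 48.8%, below 50%.
- 13/18: Beta(13, 6) gives 54.5%, above 50%.

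So 13 is the smallest count that meets the rule. P(X ≥ 13) for X ~ Bin(18, 0.5) is 4.8%. The threshold is correct and is not in question. Since 12 fails and 13 passes, reclassifying one patient can reverse the verdict.

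**2. Which reduced doses could fall short.** Assume dose proportionality and a starting dose predicted to give s% of target. Section 1.5.4 reports kinetics independent of dose, but Section 2 says that intermediate-dose kinetics still need characterisation, so this is an illustration.

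| Change (t.d.s.) | Exposure | At s = 100 | Reaches 50% of target when |
|---|---|---|---|
| 600 to 400 mg | 2s/3 | 67% | s ≥ 75 |
| 600 to 200 mg | s/3 | 33% | s ≥ 150 |
| 400 to 200 mg | s/2 | 50% | s ≥ 100 |

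With an on-target start, one step down from 600 or 400 mg may still qualify under a 50–150% window. Two steps from 600 mg do not.

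**3. How far the two counts can differ.** Suppose 12 patients complete at the starting dose, 6 complete at a dose not predicted to reach target, and none withdraws. The literal 14.4 count is 18/18, with lower limit 0.10^(1/18) = 88.0%: pass. With the 2.2.2.1 condition it is 12/18, lower limit 48.8%: fail. The >20% rule sees 0/18. With an on-target 600 mg start and a 50–150% criterion, all 6 would need two reductions and still complete, so this is an extreme case.

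**4. Chance of reaching 13/18.** The protocol gives no expected tolerance or dose-reduction rate, so p below is an assumption. P(X ≥ 13), X ~ Bin(18, p):

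| p | 50% | 60% | 70% | 80% | 90% |
|---|---|---|---|---|---|
| P(X ≥ 13) | 4.8% | 20.9% | 53.4% | 86.7% | 99.4% |

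If 60% complete at a qualifying dose and a further 10% or 20% complete only at a non-qualifying one, the chance of passing is 20.9% with the dose condition, and 53.4% or 86.7% without it. If 90% complete at a qualifying dose, the chance is already 99.4%, and counting the others can add at most 0.6 percentage points.

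**5. The floor.** From 400 mg t.d.s., two steps give 200 and then 0 mg. From 200 mg t.d.s., the first step gives 0 mg. From 600 mg the rule works as written.

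**The case against.** The strongest reply is that the condition is already there. Section 14.4 says that it addresses each endpoint and refers to 2.2.2.1 by number; a shorthand restatement under a cross-reference need not displace the endpoint. The protocol's usage points the same way: 11.3 and Appendix 7 describe a patient who needs a reduction as one who could not tolerate the initial dose, and 9.1 ties success to the selected dose. Section 15.5 also promises a full analysis plan before any analysis. This stands in part. A reader might infer that 14.4 contradicts 2.2.2.1, and the documents do not support that. What remains is that the protocol fixes a counting rule for a primary endpoint with part of the endpoint left out, and nowhere says how a dose-reduced completer is classified.

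A reader might also infer that every dose-reduced completer should be excluded. That does not follow: 2.2.2.1 speaks of a dose predicted to reach target, not of the starting dose, and a single step may still qualify.

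Nor do the documents show that a false pass is likely. They expect good tolerance: 9.2.3 says that the anticipated doses are well tolerated in other populations, and 1.5.2 reports little toxicity at 800–1600 mg/day. Those are different patients, so the rate here is unknown, but the unfavourable scenarios above are assumptions.

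Troughs on Days 8 and 14 (3.2.1.2) and recorded doses would bring low exposure to light, though outside the 13/18 count. On the floor, Appendix 7 stops at 200 mg t.d.s. and the two-step sequence is only an example, so a reader should not infer that a 0 mg dose is intended.

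**Conclusion.** The point holds as an omission. Applied literally, the 14.4 rule can credit towards 13/18 a patient who ends on a dose no longer predicted to reach target, and no other rule corrects that count. The clear case is two reductions from 600 mg t.d.s., about 33% of target; this rests on dose proportionality and an on-target start. One such patient can change the verdict at the 12/13 boundary. The expected effect cannot be sized from the protocol: it could be large if tolerance of the selected dose is near 60% and reductions are common, and is negligible near 90%. The missing floor matters only if Stage 2 starts below 600 mg t.d.s. Severity is minor to moderate.

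**What to change.** In 14.4, count towards 13/18 only patients who complete Day 14 at a dose level that the Stage 1 results predict to give 50–150% of target exposure. Report completers at lower levels separately, by dose level.

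In 11.3 and Appendix 7, state that 200 mg t.d.s. is the lowest level and that a patient who does not tolerate it is withdrawn for toxicity and counted in the >20% rule. That means two reductions from 600 mg, one from 400 mg and none from 200 mg.

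The cost is one or two sentences in 14.4 and one line in each of the other two places. No new data or visits are needed, because drug administration is already recorded (14.3). The downside is a possibly less favourable tolerability count. The wording should be settled before Stage 2 data are seen.

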15 STATISTICS

15.3 Sample Size

In the absence of data necessary to make an informed power calculation for the secondary efficacy endpoint, this sample size for this study was arrived at empirically but is supported by clinical experience and/or simulated data, as outlined below.

In a group of 36 patients randomised 1:1 between intervention and control we would have 90% power to demonstrate an effect size of -1.00 between the two groups, and 80% power to demonstrate a difference of -0.85. In the context of the endpoint being final dexamethasone dose on Day 14, scenarios that would result in this effect size or greater are clinically reasonable (see below).

Final Dexamethasone dose	
+ placebo	+ progesterone

Mean	SD	Mean	SD	SD (pooled)	Effect size	N (per arm)	N (total)
4	2	2	2	2	-1.0	18	36
4	1	2	1	1	-2.0	6	12
2	1	1	1	1	-1.0	18	36

To further illustrate the potential effect sizes that we would be able to identify, and to assess the power that $n=36$ would provide for the *cumulative* dose of dexamethasone across the study period, simulated data have been generated, based on assumptions drawn from clinical experience. In these data the mean effect size (1000 simulations) for the final and cumulative dexamethasone doses was -0.88 and -1.04 respectively. The power that we have to detect effect sizes of this magnitude with $n=18$ (per arm) is 83.05% and 92.13% respectively.

A one sided t-test was used to calculate the sample size as we are testing specifically for reduction rather than a difference. The one sided t-test is exploratory and the primary outcome is safety.

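### Safety of progesterone is called primary, but the only clinical side-effect analysis stated covers dexamethasone-related effects, in 14-day completers, with a 10% table whose denominator is not given

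*Protocol*

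**What the plan says.** - **Aim.** Section 2.1.1 includes, as a primary aim for Stage 2: "Establish the acceptability, tolerability and safety of a dose of micronised progesterone that achieves the target drug exposure".
- **Sample size.** Section 15.3 ends: "The one sided t-test is exploratory and the primary outcome is safety".
- **Primary endpoints.** Section 2.2.2.1 has two: at least 13 of 18 "patients able to tolerate micronised progesterone until the end of the 14-day treatment period", and trough concentrations within a band around target. Neither summarises adverse events.
- **Side-effect analysis.** In 14.4 Final analysis, under the Stage 2 secondary endpoint: "Dexamethasone related side-effects will be coded according to the CTCAE toxicity criteria". The text continues: "These data will be presented in several ways, including worst value over the trial period for each patient". It then adds a tabulation of effects of grade 1 or above found "in at least 10% of patients".
- **Other safety output in 14.4.** The tertiary items are "Presentation of relevant lab results to assess endocrine, liver function and lipid profiles in patients on progesterone" and a progesterone-versus-placebo comparison of imaging.
- **Population.** Section 15.5 runs the final analysis on patients who completed the 14-day treatment period and were not later found ineligible.
- **Withdrawals.** Section 10 replaces patients who withdraw because of progesterone toxicity, but keeps them evaluable for tolerability. It calls the combination unacceptably toxic if such withdrawals exceed 20% of patients.
- **Data.** Section 12.2 has every adverse event recorded, graded by CTCAE version 5 and assessed for relatedness.

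**The concern.** The trial randomises against placebo and records all adverse events, so it can show what progesterone adds to dexamethasone. The stated analysis does not do this. It selects side-effects by attribution to the background drug, which is not the IMP, and places them under a secondary endpoint. No listed analysis covers adverse events attributed to progesterone, or adverse events whatever their cause.

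The completer rule in 15.5 compounds this. Someone who stops progesterone because of an adverse event is among the most informative patients for safety, and that rule removes them. Section 10 brings them back for the tolerability count, but says nothing of the side-effect results. A reader of the final report could therefore learn how many patients stopped without seeing, in the stated tables, what they experienced.

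At stake is the safety basis for the definitive trial. Section 9.1 lists confirming acceptability, tolerability and safety among the success criteria.

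**Working it through.** **1. The plan's own figure.** The one numerical criterion close to safety is 13 of 18 tolerating treatment, said in 14.4 to show that more than 50% tolerate it using an 80% CI. The exact (Clopper-Pearson) 80% lower limit is 0.545 for 13/18 and 0.488 for 12/18, so 13 is the right count. This figure is sound, but it counts patients who continue and does not describe adverse events.

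**2. Which data reach which analysis, as written.**

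| Data | Analysis named in 14.4 | Toxicity withdrawals included? | By arm? |
|---|---|---|---|
| Tolerating to Day 14 | Count against 13/18 | Yes, by section 10 | Progesterone only |
| Dexamethasone-related side-effects | Worst value per patient; 10% table | No, by 15.5 | Not stated |
| All other adverse events (12.2) | None named | – | – |
| Endocrine, liver, lipid results | Presentation | No, by 15.5 | Progesterone only named |
| CT/MRI | Comparison | No, by 15.5 | Yes |

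**3. How many withdrawals could be missing from the side-effect results.** The rule in section 10 acts above 20% and does not state its denominator. If it is 18 patients, 20% is 0.20 × 18 = 3.6, so three withdrawals (3/18 = 16.7%) do not trigger it and four (22.2%) do. If it is 36, 20% is 7.2, so seven (19.4%) do not trigger it. Between three and seven patients could thus stop for toxicity, leave the rule unmet, and be outside the side-effect tables.

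**4. The 10% table.** The smallest count that qualifies is 10% of n, rounded up.
- Per arm: 0.10 × 18 = 1.8, so two patients are needed; a count of one (5.6%) drops out.
- All patients: 0.10 × 36 = 3.6, so four are needed; counts of one to three (up to 8.3%) drop out.

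The relevant probability is that an effect is seen but not tabulated. Per arm this is P(X = 1) = 18 × p × (1 − p)^17. At p = 0.05 it is 18 × 0.05 × 0.95^17 = 0.376. Over all 36, with the same rate in both arms, it is P(1 ≤ X ≤ 3). The true rates below are assumptions; the protocol gives none.

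| Assumed true rate | Seen but omitted, n = 18 | Seen but omitted, n = 36 |
|---|---|---|
| 5% | 0.38 | 0.74 |
| 10% | 0.30 | 0.49 |
| 20% | 0.08 | 0.05 |

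One event in 18 patients is compatible with a true rate of up to about 27% (upper limit of the exact 95% CI), so a single occurrence is not evidence that an effect is rare.

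**The case against.** The strongest reply is that adverse-event tables are normally left to the statistical analysis plan. Section 15.5 promises one, and it is not shown. The list in 14.4 is open-ended, so it does not forbid a fuller summary. This stands: the absence of a further table would not, by itself, be a defect. What does not belong to a later document is the conflict already in the protocol. Safety is primary in two sections and absent from the primary endpoints as a summary of events. The side-effect analysis that is stated is restricted by attribution, and the general population rule is restricted to completers.

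Progesterone safety is also not unexamined. There are the tolerability count, the laboratory and imaging outputs, the 20% toxicity rule, SAE reporting (12.3) and review by the data monitoring committee (5.3). Tolerability is a reasonable working measure of part of the primary aim, and attribution under blinding protects against bias.

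Three stronger readings are tempting but not supported:
- **That the 10% cut-off hides progesterone harms.** It governs only the dexamethasone-related table. Progesterone events lack a stated analysis because none is named. Even for dexamethasone effects, the same sentence presents each patient's worst value without a cut-off.
- **That 3 of 18 on progesterone against 0 of 18 on placebo would be omitted.** This needs a denominator of 36, which the text does not state, and an effect classed as dexamethasone-related.
- **That a 5% effect has a 77% chance of being left out.** The figure P(X ≤ 1) = 0.774 includes 0.397 for no event at all, where there is nothing to omit. Seen but omitted is 0.774 − 0.397, about 38%.

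**Conclusion.** The point holds in a limited form. Followed as written, the protocol's side-effect results are confined to dexamethasone-related effects in patients who completed 14 days. Patients who stopped for toxicity are left out of them, and the placebo arm is not used to compare adverse events regardless of attribution. This does not match a plan that calls safety primary.

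The 10% cut-off is secondary. It affects one of several presentations of dexamethasone-related effects, and its meaning depends on a missing denominator (two patients or four). The 38% figure assumes a true rate of 5% and a denominator of 18. The count of possible missing withdrawals, three to seven, assumes a denominator of 18 or 36 for the toxicity rule and that 15.5 is applied literally to the side-effect tables.

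This is an improvement worth making rather than a threat to the trial. The data are collected, and nothing prevents a fuller safety summary.

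**What to change.** - **15.5 Analysis Plan:** state that safety is analysed in every patient who took at least one dose of IMP, including those who withdrew or were replaced. The completer population can remain for the other analyses if the sponsor wishes.
- **14.4 Final analysis:** summarise all adverse events by arm and worst CTCAE grade, regardless of attribution and with no frequency cut-off. The dexamethasone-related presentation can stay as an addition. If its 10% table is kept, name the denominator.
- **2.2.2.1:** add this safety summary to the Stage 2 primary endpoints, so that it agrees with 2.1.1 and the closing statement of 15.3.

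The cost is a longer table and a wording change. Section 12.2 already has all adverse events recorded and graded after consent and up to 30 days after the final IMP dose, so no new data, visits or patients are needed.

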Randomisation is proposed as there are insufficient historical data on which to base estimates of the “average” reduction in dexamethasone dose in this population over the study period nor of the variability in that dose. Statistical comparison of dexamethasone dosing in the control and micronised progesterone arms is not planned. The control arm will, however, act as a comparator when evaluating dexamethasone dosing in the progesterone arm. While this study is not powered to perform formal statistical analyses, we plan to carry out exploratory work to compare the (i) cumulative dexamethasone dose (ANOVA/t-test or Mann Whitney U if the data are not normal); (ii) final dexamethasone dose (ordered logistic regression) and (iii) time to reach final dose in each arm (Cox regression). The comparator arm will also aid statistical design of the planned, subsequent definitive efficacy trial. Patients in the control arm will receive placebo provided by the manufacturer. This number of patients was chosen empirically, but is similar to the size of a typical “expansion cohort” in Phase 1 oncology trials that seek to better characterise toxicity and inform the design of a future trial; the use of such cohorts appears to increase the likelihood of success in that future trial (60).

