15.4 Randomisation and Stratification

After ensuring that the patients meet **all** eligibility criteria and has consented to participate in the study, sites will randomise the patient following the instructions described in the PROSSPER work instructions for sites. Once a patient has been randomised, a patient study number will be issued and this should be used in all correspondence.

Stage 2 of the PROSSPER trial will be randomised into two treatment groups: Progesterone arm or placebo arm. Randomisation will be a 1:1 allocation; 18 patients in each group stratified by clinical site (Leeds and Liverpool).

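### Stage 2 is randomised within site, but the named comparison of cumulative dexamethasone dose has no site term: a free, low-priority improvement to an exploratory analysis

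*Protocol*

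**What the plan says.** **Design.** Protocol section 15.4: "Randomisation will be a 1:1 allocation; 18 patients in each group stratified by clinical site (Leeds and Liverpool". The trial summary and section 2 say the same.

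**Named analyses.** Section 2 lists, as exploratory work, "cumulative dexamethasone dose (ANOVA/t-test or Mann Whitney U if the data are not normal". Here the methods are not marked as examples. Section 14.4 (Final analysis) repeats them as examples: "Comparison of cumulative dexamethasone dose in the progesterone and placebo arms (e.g. by ANOVA/t-test or Mann Whitney U if normality assumptions are violated". The other two dexamethasone comparisons are also given by example: "Comparison of final dexamethasone dose in the progesterone and placebo arms (e.g., by ordered logistic regression" and "Comparison of time to reach final dose in each arm in the progesterone and placebo arms (e.g., Cox regression". Site appears in none of these lines.

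**Sizing.** Section 15.3: "A one sided t-test was used to calculate the sample size as we are testing specifically for reduction rather than a difference". It quotes 90% power at an effect size of 1.00 and 80% at 0.85 with 18 per arm. For simulated final and cumulative doses it quotes 83.05% at 0.88 and 92.13% at 1.04.

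**Status.** Section 2 says the study is not powered for formal analyses, section 11.8 rules out a formal efficacy comparison, and section 15.3 calls the t-test exploratory. Section 15.5 sets 80% intervals and a one-sided 0.05 threshold, and promises a full statistical analysis plan.

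**The concern.** Stratified randomisation balances the arms within each site, so a site difference in dose cancels out of the arm comparison. A two-sample t-test, or a one-way ANOVA on arm (the same test when there are two arms), does not know this. It leaves the site difference in the residual variance and reports a standard error larger than the true one. Mann-Whitney U has no place for a stratum, so moving to it when normality fails also drops site. Dose moves in 2 mg steps and may reach 0 mg, so that route is a realistic one.

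At stake is precision in a trial of 36 patients. Section 2 says the comparator arm is meant to help design the definitive trial. A pooled SD that contains an unmodelled site difference would be larger than that trial needs to assume if it adjusts for site.

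**Working it through.** **1. The plan's own figures.** One-sided t-test, alpha 0.05, n = 18 per arm, df = 34, noncentrality d·√(n/2) = 3d.

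| d | Stated power | Recomputed |
|---|---|---|
| 1.00 | 90% | 90.2% |
| 0.85 | 80% | 80.3% |
| 0.88 | 83.05% | 82.7% |
| 1.04 | 92.13% | 92.1% |

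All reproduce. Between d = 0.85 and 0.88 power rises about 0.8 points per 0.01, so rounding of the effect size (±0.005) covers the 0.35-point gap at 0.88.

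**2. Inputs for the site question.** Section 15.3 gives SD 2 mg for final dose (first table row) and effect size 0.85, so the arm difference is 0.85 × 2 = 1.7 mg. Section 3.1.6 expects one patient a month at each site, so about 18 per site; with stratification, 9 per arm per site. The site difference Δ in mean dose is assumed.

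**3. Why the unadjusted test is conservative.** Let w be the within-site SD. The true standard error of the arm difference is w·√(2/18) = w/3. The t-test's pooled variance has expectation w² + (18/17)·Δ²/4. Hold that total at 2² = 4.

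- Δ = 1 mg: w² = 4 − 0.265 = 3.735, w = 1.933. The true SE is 0.644; the t-test reports about 2/3 = 0.667.
- Δ = 2 mg: w² = 4 − 1.059 = 2.941, w = 1.715. The true SE is 0.572; the t-test again reports about 0.667, which is 17% too large.

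**4. Power and error rate.** The adjusted test has effect size 1.7/w and df = 33. Its power comes from the noncentral t; the unadjusted test was simulated.

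| Δ | 1.7/w | Power, no site | Power, arm + site | True alpha, no site |
|---|---|---|---|---|
| 0 | 0.850 | 80.3% | 80.3% | 5.0% |
| 1 mg | 0.880 | 81% | 83% | 4.4% |
| 2 mg | 0.991 | 84% | 90% | 2.8% |

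If the 2 mg is read as the population SD (w² = 4 − Δ²/4), the last two rows become 81% against 82.5% with alpha 4.5%, and 83% against 89% with alpha 2.9%. Either way the unadjusted 80% interval is about 3% wider at 1 mg and 16% to 17% wider at 2 mg.

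**5. The other reading of the SD.** If the planned SD is the within-site SD, a site difference lowers the unadjusted power below the stated value, while adjustment holds it there. Site differences here are in within-site SDs.

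| Site difference | d = 1.00: no site / with site | d = 1.04: no site / with site |
|---|---|---|
| 0 | 90.2% / 90.2% | 92.0% / 91.9% |
| 0.5 SD | 89.2% / 90.1% | 91.1% / 92.0% |
| 1 SD | 86.4% / 90.5% | 88.5% / 91.9% |
| 2 SD | 71.3% / 90.1% | 75.7% / 92.2% |

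A 24/12 split between sites gives much the same result (86.7% against 90.3% at 1 SD, d = 1.00).

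**6. Scale.** The millimetre-by-millimetre counterpart for cumulative dose cannot be computed, because the protocol gives no SD for it. In SD units the argument carries over; the 1.04 column above uses the protocol's own effect size for cumulative dose.

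**The case against.** The strongest reply is that model terms are ordinary content for the statistical analysis plan, which section 15.5 promises and which is not at hand. Nothing in the protocol says that site will be ignored. Section 14.4 offers its methods only as examples, and ANOVA, ordered logistic and Cox models can all carry site. This stands in large part. What remains is that section 2 names the cumulative-dose methods without marking them as examples, and that Mann-Whitney U cannot carry site. An analysis plan that followed section 2 literally would not use the randomisation strata.

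The comparison is also exploratory. The Stage 2 primary endpoints are tolerability and trough concentration, and site adjustment in these comparisons does not touch them. That stands and sets the priority.

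Several stronger readings are tempting and are not supported:

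- A reader might infer that the protocol fixes an unstratified analysis for all three dexamethasone outcomes. It does not; the firm wording covers cumulative dose, and the regression methods leave room for site.
- A reader might infer that the stated power is wrong or that false positives increase. The power figures reproduce, and the error rate falls.
- A reader might hold that a site difference is likely. Section 11.2 does leave room for clinical judgement, but both sites follow the same blinded taper in 2 mg steps, and the protocol gives no site data.
- A reader might also ask for the pre-entry dexamethasone dose as a covariate. That is a separate matter of uncertain value: section 11.2 allows 4 to 12 mg before randomisation, while Appendix 5 shows 8 mg on Days -2 and -1, so its usable spread is unclear.

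**Conclusion.** The point holds in a limited form. Randomisation is stratified by site, and the method named for cumulative dexamethasone dose does not use site. If the sites differ, the consequence is a conservative test and wider intervals. With total SD 2 mg and effect size 0.85, the power forgone is about 2 points at a 1 mg site difference and about 6 points at 2 mg. The latter difference exceeds the 1.7 mg treatment effect itself. With no site difference the cost and the gain are both nil. These sizes rest on an assumed site difference, on equal numbers per arm within each site, and on the final-dose scale. No stated figure needs correcting and no primary conclusion is at risk. This is a free improvement of low priority.

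**What to change.** - In section 2 and section 14.4 (Final analysis), name a linear model with arm and site for cumulative dexamethasone dose, and the site-stratified Wilcoxon (van Elteren) test in place of Mann-Whitney U if normality fails.
- Include site as a covariate in the ordered logistic model for final dose and as a stratum in the Cox model for time to final dose.

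The cost is wording and one degree of freedom in the linear model (33 instead of 34); no new data are needed and the sample size stands. The odds ratio and hazard ratio then become within-site estimates, which the analysis plan should say.
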